Sampling and sample size; Any SHCP currently studying and working in COVID-19 units. Pilot research identified significant impact on student communication and a medium effect size is expected. Using Cohen's (1988) tables with an alpha of 0.01, $d = 0.5$ (a medium effect) and beta of 0.9 we will recruit 94 SHCP per group to take part in this research. This will give a total of 120 SHCP and we will add in a 10% margin ($n=20$) for dropout or incomplete data. This gives a total of 140 SHCP to be randomised per arm or 280 in total. We will try and ensure a mixed sample with SHCP from different allied health professional groups using purposive sampling.

Sequence generation; Random number calculator with randomly selected block sizes (Efird, 2011).

Allocation concealment; undertaken by e-links not known to the researcher

Sequence generation; We will replicate the pilot research and include a random number calculator with randomly selected block sizes (Efird, 2011). Randomisation undertaken by a member of the research team separate from the study will allocate SHCP to an intervention control group using a random number generator.

Blinded assessor; Only blinded assessment will take place. Before randomisation a blinded assessor (lecturer in physiotherapy or research student) will distribute questionnaires. The pre-recorded e-learning programme has been prepared by [name] who developed and prepared all pilot studies. Following the completion of the training an assessor who is blinded to treatment arm will organise and collect follow-up assessments.

Data collection methods: Before data collection starts SHCP will be shown the information sheet via email and asked to consent (Appendix B). A baseline measurement will take place (Appendix C). The baseline measurement will take place over a secure electronic data capture system called Research Electronic Data Capture (REDCap). Following this, students in each group will receive the training. Once the training is complete students will again fill in the measurement tools using REDCap. The research associate will send out two email reminders to any participant who doesn't fill in the forms.

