Intervention: The SIT intervention will include a single screening interview taking 20 minutes with [name]. Following this the participant will be sent a pre-recorded e-based training session. The lecture takes 45 minutes. The indicative content considers examples of interactions, the science behind the MEAH, the use of screening and how to engage in a brief narrative-based intervention within practice. It has the same components as the pilot studies, although adapted into one training session. The final part of the training for SHCP will include an e-learning presentation. The presentation will provide an analysis of the screening calls. This will reveal the most common difficulties and stories expressed within screening and will

summarise the difficulties that were challenging to adapt to, illustration of how the MEAH is important for this understanding and the most common coping strategies identified (this was undertaken and achieved as part of the pilot research to consolidate learning). The principles are that sharing this information will provide direct access to others experiences which has been associated with enhanced mental health outcomes (Ooms et al., 2016; Soundy et al., 2019). The benefit of this is SHCP can access effective coping strategies that promote mental health and psychological well-being outcomes. This entire process will take a maximum of two hours to complete at a pace and time that is convenient to the participant.

Inactive control group 1: an inactive waiting list control group will be used. Individuals in this group will receive or be offered the SIT intervention at week 12.

Active control group 2: an alternative e-intervention will be used which includes a 45 minutes pre recorded lecture. Individuals in this group will receive or be offered the SIT intervention at week 12.

Outcome measures for SHCP;

See Appendix C for all outcome measures

Demographics; Age, gender, professional group, type of course, year of course. Time experience of working in a COVID-19 setting in months.

Primary outcome measure for SHCP:

The Hospital Anxiety and Depression Scale (HADS: Zigmond and Snaith, 1983). A 14-Item questionnaire that assesses depression and anxiety.

Secondary outcomes measures for SHCP;

(a) The SF-12 Quality of life questionnaire (Ware et al., 1995). A 12-item questionnaire that assesses quality of life.

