Appendix A

Initial Email Advertising training

Subject Title: Mental Health Screening, intervening and Training (SIT) of Health Care Professionals; a randomised control trial

Message content:

We are looking for student health care professionals to take part in a new study designed to support mental health and patient interaction.

The assessments if you joining the study take a total of 10 minutes on three occasions (pre, post and 12-week follow up)

IF you take part in the study you could be allocated to a control group or intervention group

If you get allocated to the intervention group:

The total training time takes 2 hours that can be completed at a self-pace online (undertaken as suits you). The training has 3 parts

- 1. Arrange a e-based screening call with [name] (zoom or skype or telephone) to support you and your mental health**
- 2. Watch a pre-recorded 45 lecture to train you**
- 3. Consider a summary e-presentation of the responses given across health care professionals to part 1.**

If you get allocated to the control group

You will either view a 45 minute lecture or be allocated to a no treatment control

Document provided to participants if it is identified that they are distressed or become concerned following the intervention.

Appendix C: Questionnaire pack given across email to SHCP at pre-post and follow up time points trial.

Unique Identification Number Generated for you: MEAH 02 A (CHANGED FOR EACH PARTICIPANT)

Please complete this questionnaire which asks specific questions about the course content and your reflections of the value of the course.

PLEASE NOTE BY COMPLETING THIS QUESTIONNAIRE YOU ARE PROVIDING CONSENT FOR YOUR PARTICIPATION. Please contact [name] should you want your data removed by 1 August 2020.

Demographics

Age (Years)	
Gender	
Name of Profession (e.g., Nurse, Physiotherapist)	
Type of Course: BSc, MSc	
Year of Course:	
Have you had experience within a COVID-19 unit	Yes / No
Have you had experience of caring for people with COVID-19 as part of your role	Yes / No
Have you had past teaching or experience related to psychological adaptation, hope, emotions or illness stories (narratives)? (circle one)	YES / NO

Hospital Anxiety and Depression Scale (HADS)

Tick the box beside the reply that is closest to how you have been feeling in the past week. Don't take too long over you replies: your immediate is best.

I feel tense or 'wound up':

Most of the time	3
A lot of the time	2

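### The protocol says all assessment is blinded, but every quantitative outcome is self-rated by participants who are not masked, and the recruitment email makes the control arms easy to recognise

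*Protocol*

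**What the plan says.** The Blinded assessor paragraph of the protocol's Main Study section opens with "Only blinded assessment will take place". It then gives that person's tasks. At the start: "Before randomisation a blinded assessor (lecturer in physiotherapy or research student) will distribute questionnaires". After training: "Following the completion of the training an assessor who is blinded to treatment arm will organise and collect follow-up assessments".

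Under Data collection methods, the scores come from the participants: "Once the training is complete students will again fill in the measurement tools using REDCap". The primary outcome, HADS, is introduced as "A 14-Item questionnaire that assesses depression and anxiety", and its instructions in Appendix C ask respondents to report their own feelings over the past week.

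Appendix A, the email sent to all prospective participants, says "IF you take part in the study you could be allocated to a control group or intervention group". It lists three parts for the intervention group: a screening call described as supporting the participant's mental health, a lecture, and a summary presentation. For the control group it says "You will either view a 45 minute lecture or be allocated to a no treatment control".

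**The concern.** Assessor blinding protects an outcome when the assessor makes a judgement that knowledge of the arm could sway. Here the blinded person makes none. Self-rated anxiety and depression are open to expectation, and to disappointment at not receiving the treatment of interest, and the people giving these ratings are not masked. A reader of the protocol, or of a report that repeats its wording, would credit the trial with a protection that its outcomes do not have. The protocol commits to SPIRIT and CONSORT, so the statement is likely to carry into the report.

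The email matters for a second reason. An active control can make expectation more alike between arms, which a waiting list cannot do. Naming the lecture as a control, in the same line as no treatment, works against that.

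**Working it through.** The protocol gives no figure on this point to reproduce, so the check is mainly a comparison of its statements.

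**Step 1: who produces each score.** HADS, SF-12, the Open Minds scale, the Froehlich Communication Survey, the Interpersonal Reactivity Index, the Adult Hope Scale and the MEAH tool are all printed in Appendix C as forms that respondents complete about themselves. None is rated by an observer.

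**Step 2: what the blinded person does.** The stated tasks are to distribute, organise and collect. None of these enters a score.

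**Step 3: whether anything masks the participant.** The Allocation concealment line concerns links not known to the researcher, which says nothing about participants. No other text shown masks them.

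**Step 4: whether participants can recognise their arm.** The content comes from the Intervention and control-group paragraphs of the Main Study, and the labels from Appendix A.

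| Arm | Content before week 12 | Label in Appendix A |
|---|---|---|
| SIT | 20-minute call, 45-minute lecture, summary presentation; at most two hours in all | Intervention group |
| Active control | 45-minute lecture | Control group |
| Inactive control | Nothing | Control group, no treatment |

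A participant who receives a lecture but no call and no summary presentation can match that to the control description. A participant who receives nothing can do so with certainty. Both control groups are also offered SIT at week 12, which is a further cue.

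**Step 5: illustration of sensitivity, on assumed values only.** The documents give no size for expectation-driven reporting. Suppose that there is no true effect, that self-rating shifts the difference between two arms by b standard deviations, and that two means are compared at the protocol's alpha of 0.01, two-sided. With n per arm:

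- SE = √(2/n), in SD units: 0.129 for n = 120 and 0.120 for n = 140.
- Rejection probability = 1 − Φ(2.576 − b/SE) + Φ(−2.576 − b/SE).

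| Assumed b | n = 120 per arm | n = 140 per arm |
|---|---|---|
| 0 | 1.0% | 1.0% |
| 0.1 | 3.6% | 4.1% |
| 0.2 | 15% | 18% |
| 0.3 | 40% | 47% |

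Relative to the planned effect of d = 0.5, these shifts are 0.1/0.5 = 20% to 0.3/0.5 = 60%. Both 120 and 140 appear in the sample-size paragraph and are read here as per-arm numbers. That paragraph gives more than one figure, which is a separate matter. The table shows only that a modest shift would count; it is not evidence that one exists.

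**The case against.** The strongest defence is that the sentence stands in a paragraph about the assessor and is narrowed by what follows. On that reading it claims only that staff who handle questionnaires are blind to arm. This may well be true, and the protocol nowhere claims that participants are blinded. That stands as far as staff are concerned. It does not rescue the sentence as written, which covers all assessment when the assessment is done by the participants.

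Participants in a behavioural trial can rarely be masked in full. That also stands. The lack of participant blinding is not the fault here; the inaccurate statement and the avoidable labelling are.

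The email's contrast between arms is milder than it may look. The mention of mental health belongs to the screening call alone, the lecture is presented as training, and the email introduces the whole study as supporting mental health before it names any arm. This tempers the point, but the control label remains.

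A reader might also infer that participants are told their own allocation. The protocol does not say so: the email describes the possible arms in advance, and recognition of the arm is a strong inference from content. The information sheet (Appendix B) is not in the text available, so what it says about allocation is unknown.

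**Conclusion.** The point holds in this form: the blanket blinding statement does not fit the outcomes as measured and should be corrected. The recruitment wording adds cueing that could be reduced at little cost. The conclusion rests on all seven quantitative measures being self-completed, which the protocol shows, and on no masking of participants, since none is described.

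The size of any bias cannot be estimated from the documents. The likelier direction is in favour of SIT, but the documents do not establish this.

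It is tempting to conclude that the active control has lost its purpose. The documents do not support that. The protocol gives no rationale for the arm, and a 45-minute pre-recorded lecture still controls in part for e-learning format, time and study attention. Its control of expectation is weakened, not removed.

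**What to change.** Replace the opening sentence of the Blinded assessor paragraph with: *Outcomes are self-reported by participants who are not blinded; staff who distribute and collect questionnaires are blind to arm.* Mention blinding of the analyst only if the sponsor adopts it, because nothing in the protocol says so now.

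In Appendix A, and in the information sheet if it uses the same wording, describe the arms neutrally, for example as an online training package with a call, an online lecture package, and a delayed start. Drop the intervention and control labels, and do not state a benefit for one arm only. Keep the call disclosed, since people need to know of it before they consent.

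The cost is one protocol sentence, a reworded email and an ethics notification. The report must also concede unblinded self-report. The rewording solves only part of the problem: waiting-list participants will know their status under any wording, and the two active packages will still differ in content and length.

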From time to time, occasionally	1
Not at all	0

I still enjoy the things I used to enjoy:

Definitely as much	0
Not quite so much	1
Only a little	2
Hardly at all	3

I get a sort of frightened feeling as if something awful is about to happen:

Very definitely and quite badly	3
Yes, but not too badly	2
A little, but it doesn't worry me	1
Not at all	0

I can laugh and see the funny side of things:

As much as I always could	0
Not quite so much now	1
Definitely not so much now	2
Not at all	3

Worrying thoughts go through my mind:

A great deal of the time	3
A lot of the time	2
From time to time, but not too often	1
Only occasionally	0

I feel cheerful:

Not at all	3
Not often	2
Sometimes	1
Most of the time	0

I can sit at ease and feel relaxed:

Definitely	0
Usually	1
Not Often	2
Not at all	3

I feel as if I am slowed down:

Nearly all the time	3
---------------------	---

Very often	2
Sometimes	1
Not at all	0

I get a sort of frightened feeling like 'butterflies' in the stomach:

Not at all	0
Occasionally	1
Quite Often	2
Very Often	3

I have lost interest in my appearance:

Definitely	3
I don't take as much care as I should	2
I may not take quite as much care	1
I take just as much care as ever	0

I feel restless as I have to be on the move:

Very much indeed	3
Quite a lot	2
Not very much	1
Not at all	0

I look forward with enjoyment to things:

As much as I ever did	0
Rather less than I used to	1
Definitely less than I used to	2
Hardly at all	3

I get sudden feelings of panic:

Very often indeed	3
Quite often	2
Not very often	1
Not at all	0

SF-12®:

Answer every question by placing a check mark on the line in front of the appropriate answer. It is not specific for arthritis. If you are unsure about how to answer a question, please give the best answer you can and make a written comment beside your answer.

1. In general, would you say your health is:

Excellent (1)

Very Good (2)

Good (3)

Fair (4)

Poor (5)

The following two questions are about activities you might do during a typical day. Does YOUR HEALTH NOW LIMIT YOU in these activities? If so, how much?

2. MODERATE ACTIVITIES, such as moving a table, pushing a vacuum cleaner, bowling, or playing golf:

Yes, Limited A Lot (1)

Yes, Limited A Little (2)

No, Not Limited At All (3)

3. Climbing SEVERAL flights of stairs:

Yes, Limited A Lot (1)

Yes, Limited A Little (2)

No, Not Limited At All (3)

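### The protocol defines the primary outcome as a 14-item HADS, but the questionnaire pack in Appendix C prints only 13 HADS items and gives no rule for scoring 13

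*Protocol*

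**What the plan says.** Under the primary outcome heading, the protocol names the HADS and describes it as "A 14-Item questionnaire that assesses depression and anxiety". The outcome section opens with the instruction "See Appendix C for all outcome measures", so the appendix is where the instruments are fixed. That appendix is titled "Appendix C: Questionnaire pack given across email to SHCP at pre-post and follow up time points trial".

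On capture, the data collection section states: "The baseline measurement will take place over a secure electronic data capture system called Research Electronic Data Capture (REDCap"). It says the post-training measures are also completed in REDCap. The REDCap form itself is not reproduced.

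In Appendix C the HADS block starts with "I feel tense or 'wound up" and ends with "I get sudden feelings of panic". The SF-12 heading comes directly after that item's four response options. The protocol nowhere mentions a shortened HADS, a deliberate omission, or a scoring rule for fewer than 14 items.

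**The concern.** The length stated for the primary outcome and the form meant to collect it disagree by one item. HADS is the sole primary outcome and the study aim covers both depression and anxiety, so the form decides what the trial measures. If it is used as printed, the same item goes uncollected for every participant at every time point. The total would have a shorter range than the scale the protocol names, and a reader could not set the trial's means directly beside 14-item HADS results. Responses to an item that was never asked cannot be recovered later, so the time to settle this is before baseline.

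**Working it through.** **Inputs.** Stated length: 14 items (protocol, primary outcome). Printed items: counted in Appendix C between the HADS heading and the SF-12 heading. Item scoring: each printed item has four options scored 0 to 3.

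**Step 1, count the printed items.** By topic, in order:

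1. tension
2. enjoyment
3. dread
4. humour
5. worry
6. cheerfulness
7. ease
8. being slowed down
9. butterflies
10. appearance
11. restlessness
12. looking forward
13. panic

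The count is 13, so the stated 14 is not reproduced.

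**Step 2, range of the total.** Maximum = number of items × 3.

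- As stated: 14 × 3 = 42.
- As printed: 13 × 3 = 39.
- Shortfall: 42 − 39 = 3 points, or 1/14 = 7.1% of the scale.

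**Step 3, is this a loss in reading the PDF?** If text had been lost generally, other instruments in the same appendix should be short too. They are not:

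| Instrument | Stated | Printed |
|---|---|---|
| HADS | 14 | 13 |
| SF-12 | 12 | 12 (one is misnumbered) |
| MEAH version 3.3 | 5 | 5 |
| Interpersonal reactivity index | 28 | 28 (4 × 7) |
| Open Minds Scale | 15 | 15 |
| Froehlich Communication Survey | 25 | 25 |
| Adult Hope Scale | 12 | 12 |

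Only the primary outcome is short. All 13 HADS items keep their four responses, and no redaction or missing-figure mark stands in the block.

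**Step 4, which kind of item is missing?** Sorted by content, items 1, 3, 5, 7, 9, 11 and 13 concern anxiety (7 items). Items 2, 4, 6, 8, 10 and 12 concern mood or interest (6 items). The two kinds alternate, which suggests that the absent item is a mood item. This is inference: the protocol assigns no item to a subscale and does not state how the 14 items divide.

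**Step 5, effect on comparisons.** The same item is absent in all arms, so no arm is favoured. If the missing item behaves like the average of the others (assumption), raw totals and raw group differences are about 7.1% smaller than on 14 items. The standard deviation shrinks roughly in step, so a standardised difference such as the d = 0.5 used for the sample size changes little. Prorating a complete 13-item total by 14/13 restores the range (39 × 14/13 = 42) and, being a constant multiplier, leaves the standardised comparison as it was.

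A switch of form partway through would be worse than either version. A participant with 13 items at baseline and 14 later could gain up to 3 points from the form alone.

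**The case against.** The strongest objection is that the count describes text extracted from a PDF, not the source form. The response table for the item on being slowed down is visibly split, the HADS items are unnumbered, and a short table lost just before the SF-12 heading would leave no trace. This stands as a possibility. Against it, six other instruments came through at full length and every printed HADS item is complete, so an omission in the form is more likely.

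A second objection is that Appendix C may not be the operative form. Measures are completed in REDCap, and the appendix looks like an older template: its date for requesting data removal, 1 August 2020, precedes enrolment in October to November 2020. This also stands in part. It makes the consequence conditional on the REDCap build, but it does not remove the contradiction, because the protocol points to Appendix C for every outcome measure.

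A reader might go further and infer that depression scores and their group differences would be about 14% too small. That figure is 1/7 and needs a 7/7 split of items between subscales, which the documents do not state. A reader might also infer harm to caseness rates or to a comparison of anxiety with depression totals. The protocol plans no HADS cut-off and no such comparison.

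**Conclusion.** The point holds as a contradiction in the definition of the sole primary outcome: 14 items stated, 13 printed, and no scoring rule for 13. Its size is one item for every participant at every time point: a maximum of 39 instead of 42, or 7.1% of the scale. The resulting score would be a non-standard variant, not directly comparable with 14-item HADS scores. This rests on two assumptions: that the extracted text reflects the source appendix, which the other instruments support, and that REDCap follows the appendix, which cannot be checked here.

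The missing item is probably a depression item, but the documents do not establish that. The omission does not by itself bias the between-group comparison. Nor would a 13-item baseline make the outcome unusable: the lost responses stay lost, but scoring the same items throughout preserves the comparison between arms.

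**What to change.** Before the first baseline questionnaire goes out, check the source Appendix C and the REDCap build item by item against the licensed 14-item HADS. Restore the missing item wherever it is absent.

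If any baselines have already been taken with 13 items, score the same 13 items (or prorate) at all time points in all arms, and report that this was done. Do not mix 13-item and 14-item totals within participants.

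The cost is a corrected form, a minor amendment and one more question per questionnaire. If REDCap already carries 14 items, only the appendix needs correcting.

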Together these two applications (screen, intervene and train) of the MEAH model have been combined into a single e-learning approach to support the mental health of SHCP and to train SHCP to manage patients in very short time period (under 2 hours). Having completed the SIT approaches we would be able to consider effectiveness of the training during SHCP-patient interactions by focusing further on emotions, adaptation and hope.

It is important to note that all stages of the SIT approach have been developed using electronic resources, and as such the planned study methods are compliant with current legislation on social distancing, whilst being scalable to achieve a wider reach of SHCP across the NHS and other practice settings in the post COVID era across the UK. The additional benefit of this work

¹ Ethical approval was gained from University of Birmingham ethics committee reference: ERN_20-0565.

² Ethical approval was gained from University of Birmingham ethics committee reference: ERN_18-1970B and ERN_18-1970C. Online protocol number: ISRCTN 13368968

is that once trained, SHCP can apply the training at a patient level, or as part of personalised medicine and we would be able to pilot the effectiveness of the training on patients using a multi-centre quasi-experimental design.

Our research to date underpins our rigorously developed e-learning training which has been tested as a proof of concept in a single application and has the potential, following further research to be applied to the NHS and then more globally. The proposed research seeks to combine the above two applications for a novel study that can be offered across all frontline SHCP.

Aims and Objectives

The aim of this study is to investigate the impact of a 2-hour MEAH e-learning training session on depression and anxiety of SHCPs.

Objectives

1. To explore changes in depression and anxiety as a primary outcome measure across three time points (pre-intervention, post intervention, at 12-weeks) for all front-line SHCP during the screening and intervening phase. To compare the intervention and control at the pre-, post- and follow up time points
 2. To identify longer term outcomes for the SHCP intervention group at 6 months
 3. To examine changes in secondary outcome measures on SHCP including quality of life, stigma, communication, hope, and empathy.

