24-week intervention group follow up completed by: May 2021 (analysis completed by trials unit other staff costs covered by University)

Follow up publication: June 2021

Other publications: September 2021.

Data management: The research associated will use the University REDCap system to access the data and only work on a University password protected computer.

Statistical methods; For the main study and sub-study descriptive statistics will be used. Confidence intervals will be used to consider change. A factorial ANOVA (a parametric statistical technique which can assess change in one test rather than needing to perform many) will be used to test group differences across outcome measures. An ANOVA will consider the change in scores across time for the intervention group. All qualitative data will be analysed using a thematic analysis (Braun and Clarke, 2006).

Data monitoring: [name] will report any adverse events to University program leader for consideration. Any program leader will be able to stop the study if required. No adverse events were reported across all pilot research. All adverse events will be reported to the steering group committee.

Ethics: We will adhere to the; Research Governance Framework (Department of Health 2005), Declaration of Helsinki (World Health Association, 2013) and University of Birmingham Code of Practice for research (University of Birmingham 2018) and General Data Protection Regulation (2018).

Protocol amendments: [name] will report any protocol amendments.

Consent: the research associate will ensure consent is obtained from participants.

Confidentiality: All data will be stored anonymously on the University of Birmingham computer. Declaration of interest: None are declared.

Access to data: only the research team will have access to the full data.

Ancillary and post-trial care: This will be reported by [name] to program leads if required.

Deliverables

Benefits within the Hospital setting

- Reduced depression and anxiety across SHCP
- Positive changes in hope, psychological adaptation and emotions in relation to a specified difficulty
- Increased resilience and decreased burn out in staff
- Enhanced interactions that are supportive and able to empower patients to be more autonomous
- Increased patient satisfaction
- Potential to decrease reliance on pharmacological approaches
- Reduced work absence and improved work productivity
- Identification of basic NHS-related cost savings

[figure not shown]

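### One factorial ANOVA over three arms cannot show that SIT beats either control, and the SIT-only ANOVA is not a randomised comparison

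*Protocol*

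**What the plan says.** Three passages of the Protocol set the question:

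- Design, with the two control-group paragraphs: three randomised arms (SIT, an inactive waiting list and an active 45-minute recorded lecture). Both controls are offered SIT at week 12.
- Objectives, item 1: change in depression and anxiety over pre, post and 12 weeks, and "To compare the intervention and control at the pre-, post- and follow up time points".
- Sampling and sample size: "Using Cohen's (1988) tables with an alpha of 0.01", d = 0.5 and "beta of 0.9 we will recruit 94 SHCP per group to take part in this research".

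The Statistical methods paragraph then fixes the analysis. For group differences, "A factorial ANOVA (a parametric statistical technique which can assess change in one test rather than needing to perform many) will be used". Separately, "An ANOVA will consider the change in scores across time for the intervention group". Confidence intervals are planned for change. The paragraph does not say that time is a within-person factor, which effect is the test, or which control SIT is set against. Under Participant timeline, the last visit covers the SIT arm only: "24-week intervention group follow up completed by: May 2021".

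**The concern.** The reason given for the factorial ANOVA is that a single test replaces several. With three arms, that is its weakness. A significant omnibus result says that the arms do not all follow the same course; it does not say which arm differs or from which. The trial could report a positive primary result when SIT adds nothing over the waiting list, or nothing over an ordinary recorded lecture.

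The SIT-only ANOVA has a different problem. It has no comparator, so any change common to all students over the autumn and winter of 2020-21 counts as change in the SIT arm. If it were read as evidence of benefit, the randomisation would play no part in the conclusion.

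**Working it through.** **Inputs.** From the Protocol: three arms; visits at pre, post and 12 weeks; d = 0.5; alpha 0.01. Assumed, because the Protocol gives neither a HADS SD nor a correlation: SD 1, equal correlation ρ between visits of 0.3, 0.5 or 0.7, any effect present at both post and 12 weeks, two-sided tests and n = 120 per arm.

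**1. What the sample size was built for.** For two means, n per group = 2(z₁ + z₂)²/d².

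- Power 0.90: 2(2.576 + 1.282)²/0.25 = 119.04, so 120 per group.
- Power 0.80: 2(2.576 + 0.842)²/0.25 = 93.4, so 94 per group.

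The stated 94 is therefore the answer for power 0.80, while 120 per group fits 0.90. The Protocol gives 120 as a total, and that mismatch is a separate matter. What counts here is that both figures belong to a two-group contrast. I use 120 per arm below.

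**2. Valid mixed ANOVA, group-by-time F.** The noncentrality is λ = n × (sum of squared interaction effects)/(1 − ρ).

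- One arm differs from the other two: centred values 2/3, −1/3, −1/3; squares sum to 2/3.
- Effect 0, 0.5, 0.5 over the visits: centred values −1/3, 1/6, 1/6; squares sum to 1/6.
- Product 2/3 × 1/6 = 1/9. At ρ = 0.5, λ = 120 × (1/9)/0.5 = 26.67.
- The 1% critical value of F(4, 714) is 3.346, which gives a rejection probability of 96.8%.

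λ does not depend on which arm is the odd one out. The test gives the same answer in three situations:

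| Truth | Rejects at 0.01, ρ = 0.3 / 0.5 / 0.7 |
|---|---|
| Only SIT works | 86% / 97% / >99% |
| Only the lecture works; SIT equals waiting list | 86% / 97% / >99% |
| SIT equals the lecture; both beat waiting list | 86% / 97% / >99% |

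Simulation of the last two rows at ρ = 0.5 gave 96% to 97%.

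**3. If the scores were analysed as independent.** The arm mean square then has expectation 1 + 2ρ against an error of 1. With a 1% critical value of 4.625 for F(2, 1071), the null rejection rate is exp(−4.625/(1 + 2ρ)):

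- ρ = 0.3: exp(−4.625/1.6) = 5.6%
- ρ = 0.5: exp(−4.625/2.0) = 9.9%
- ρ = 0.7: exp(−4.625/2.4) = 14.6%

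The group-by-time test becomes too conservative. Its power at d = 0.5 is about 63%, 61% and 59% (simulated: 58% to 64%). By contrast, the mixed version keeps its size under equal correlation: simulated null rejection at 0.01 was 0.8% to 0.9% for group and 0.9% to 1.2% for group by time.

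**4. SIT-only ANOVA with no treatment effect.** Let every arm improve by 0.3 SD at post and 12 weeks. The centred values are 0.2, −0.1, −0.1 and their squares sum to 0.06. At ρ = 0.5, λ = 120 × 0.06/0.5 = 14.4. Against a 1% critical value of 4.695 for F(2, 238), it rejects in 81% of trials (62% at ρ = 0.3, 97% at ρ = 0.7).

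**5. Baseline-adjusted contrast of SIT with one control.** The residual variance is 1 − ρ². Power = Φ(0.5/√(2(1 − ρ²)/120) − 2.576):

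- ρ = 0.3: Φ(4.060 − 2.576) = 93.1%
- ρ = 0.5: Φ(4.472 − 2.576) = 97.1%
- ρ = 0.7: Φ(5.423 − 2.576) = 99.8%

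**The case against.** The strongest reply is that the term factorial ANOVA covers the mixed group-by-time form. The paragraph speaks of assessing change and the objectives list three visits, so time as a repeated factor is a natural reading. That stands. A reader might infer from the missing within-person term that the error rates are wrong, but the text does not commit to analysing the scores as independent, and the mixed form holds its nominal level. Step 3 shows only what the ambiguity could cost.

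A reader might also infer that baseline is thrown away. It is not: with the pre visit as a level of time, the group-by-time test uses it, though less efficiently than adjustment does. Against a valid mixed ANOVA, the power gain from adjustment is negligible at ρ = 0.5 to 0.7 and visible only at ρ = 0.3 (93% against about 86%).

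The SIT-only ANOVA is not named as the test of effectiveness. It fits Objective 2, which concerns the intervention group at 6 months, after the controls have been offered SIT. That also stands. It misleads only if it is used to claim benefit; since the sentence is not confined to 6 months, a label is needed.

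A reader might add a multiplicity charge by counting every subscale, control and visit, or say that people with a missed visit are dropped. The Protocol plans no such set of separate primary tests and fixes no missing-visit rule, so neither is supported.

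Finally, covariance structure and follow-up contrasts may sit in an SAP that is not shown. That covers missing detail. It does not cover a stated test whose stated rationale, one test in place of several, conflicts with Objective 1 in a three-arm trial.

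**Conclusion.** The point holds in limited form. On any reading, the three-arm omnibus F does not answer whether SIT beats the waiting list or the lecture, and it is not the contrast that the sample size describes. Even in valid form, it rejects in about 97% of trials (86% to over 99% across the assumed correlations) when SIT is no better than one of its controls and another difference of 0.5 SD exists. The SIT-only ANOVA cannot separate SIT from a shared trend: 81% rejection at ρ = 0.5 for a common 0.3 SD change.

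These sizes rest on 120 per arm, equal correlation between visits, effects present at both follow-up visits, and assumed values for ρ and the shared trend. The argument about the omnibus test does not depend on them; only the percentages do. The documents do not support calling the planned test invalid or its error rates wrong. Severity: should be fixed.

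**What to change.** - Make the primary analysis an ANCOVA of HADS adjusted for baseline, or a linear mixed model of the follow-up scores with baseline as covariate and a within-person covariance.
- Name two contrasts, SIT versus active control and SIT versus waiting list, at a follow-up time that the sponsor declares primary (12 weeks, for example).
- Test each at the 0.01 used for sizing. The family-wise error is then at most 2 × 0.01 = 2% for one HADS score, or 4 × 0.01 = 4% if anxiety and depression are tested separately.
- Remove the single-test rationale. If an omnibus test is kept, make it secondary and state its within-person term.
- Report change within the SIT arm and the 24-week SIT-only data descriptively, with confidence intervals and no claim of effectiveness.

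The cost is analysis wording. No visit, questionnaire or participant is added. The gain is mainly a result that can be interpreted; the gain in power over a valid mixed ANOVA is small unless the correlation is low.
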